5.1 Purpose of Clinical Study

To evaluate the safety and tolerability of the investigational product (VM202) injected in the weakened lower limb muscles of CMT1A patients.

Primary Objective

To evaluate safety and tolerability following repeated doses of the investigational product (VM202).

Secondary Objectives

To evaluate efficacy following repeated doses of the investigational product (VM202).

- (1) Changes in severity of disease
 - CMTNS-v2 (Charcot-Marie-Tooth Neuropathy Score version 2)
- FDS (functional disability scale)
- (2) Changes in lower limb function:
 - ONLS (overall neuropathy limitation score) leg scale
 - 10MWT (10-meter walk test)
- (3) Changes in fatty infiltration level of lower limb muscles:
 - MRI leg
- (4) Nerve regeneration potential:
 - CMAP (compound motor nerve action potential)
 - SNAP (compound sensory nerve action potential)
 - NCV (nerve conduction velocity)
- (5) HGF antibody generation by VM202

5.2 Clinical Study Design

[figure not shown]

Figure 7. A schematic diagram of clinical study

This is a phase 1/2a, open-label, single-center study to evaluate for 270 days the safety and tolerability of intramuscularly injected VM202 in twelve CMT1A patients with symptoms of lower limb weakening. When subjects who have voluntarily signed the informed consent form are enrolled in this clinical study, they shall undergo tests to determine their eligibility for this clinical study.

Subjects who have satisfied the inclusion/exclusion criteria shall be given the investigational product 4 times (2 administration sessions for 2 weeks followed by a 3-month safety and tolerability assessment, and then 2 administration sessions for 2 weeks) in total for 104 days. Safety and tolerability assessments shall be performed at every visit, and efficacy assessments shall be performed at the 2nd visit (baseline, Day 0, prior to administration) and the 7th visit (termination visit, Day 270).

Although this is a phase 1/2a clinical study, it is intended to evaluate clinically meaningful endpoints in relation to efficacy considering that Charcot-Marie-Tooth disease type 1A (CMT1A) is a rare disease that still does not have an available treatment method.

5.3 Subjects

5.3.1 Target Number of Subjects and Rationale for Calculation

Using this investigational product, clinical studies have been conducted on six diseases in total since 2007 (see Table 2). Although there were no cases in which the drug was applied to CMT1A patients, a total of 18 subjects were recruited in a clinical study on amyotrophic lateral sclerosis (see section 3.8.5) among these studies. As a result of assessing safety, it is intended that this clinical study be conducted with 12 subjects, which is set less than the size of subjects in the study of amyotrophic lateral sclerosis because it is just addition

of the indication and the progression of CMT1A is slow although this clinical study also targets similar symptoms.

5.3.2 Inclusion Criteria

Subjects enrolled in this clinical study must satisfy all of the following inclusion criteria:

- 1) Males or females \geq 19 years of age and \leq 65 years of age
- 2) Patients with confirmed diagnosis of CMT1A by genetic testing
- 3) Patients with mild-to-moderate severity assessed by Charcot-Marie-Tooth Neuropathy Score version 2 (CMTNS-v2) with a score > 2 and ≤ 20
- 4) Individuals with lower limb muscle weakness with minimum dorsiflexion or more
- 5) Individuals who voluntarily consented to participate in this study and signed the IRB-approved informed consent form after listening to a description on the characteristics of this clinical study prior to all screening tests
- 6) Individuals who can comply with the requirements in the clinical study
- In case of females of child-bearing potential, those who test negative in a urine or serum pregnancy test at screening
- 8) Individuals who practice medically approved contraceptive methods* throughout the clinical study

*Definitions

- · Drugs: Oral contraceptives, skin patches, or progestin formulations (implants or injections)
- · Barrier methods: Condoms, diaphragms, intrauterine devices (IUDs), vaginal suppositories
- Abstinences: Complete abstinence (However, periodic abstinence (e.g., calendar method, ovulation method, and sympto-thermal method) and self-restraint are not considered as acceptable methods of contraception.)

5.3.3 Exclusion Criteria

Subjects will be excluded from this clinical study if any one of the following criteria is met:

- 1) Patients with significant respiratory, circulatory, renal, gastrointestinal, hepatic, endocrine, hematologic, psychiatric disorders or other severe diseases, or alcohol or drug addiction who may develop safety issues or cause confusion in the interpretation of the clinical study results as determined by the principal investigator
- Patients with other neuromuscular diseases or neuropathy-inducing factors: Patients with chronic alcohol addiction, undergoing anticancer chemotherapy, or taking neurotoxic drugs

- 3) Patients diagnosed with diabetes
- 4) Patients diagnosed with inflammatory bowel disease
- 5) Patients with a history of stroke or cerebral ischemic attack within 12 months prior to the screening date
- 6) Patients with a history of coronary artery disease, such as myocardial infarction and unstable angina pectoris, within 12 months prior to the screening date
- 7) Morbidly obese patients with body mass index (BMI) ≥ 37
- 8) Patients who underwent orthopedic surgery (corrective surgery for bone and ligament, artificial joint implantation, osteosynthesis, osteotomy, arthroscopic surgery) in the lower limbs within 6 months prior to the screening date
- Patients who may be affected by the muscle strength measurement test due to ankle contracture or surgery
- 10) Patients with uncontrolled hypertension (if systolic blood pressure is ≥ 160 mmHg or diastolic blood pressure is ≥ 100 mmHg at screening)
- 11) Patients or patient's immediate family members (parents, siblings, offspring) with a history of malignant tumors within the last 5 years prior to the screening date, excluding basal cell carcinoma or squamous cell carcinoma that occurs on the skin (if it is determined that there is no possibility of relapse after resection), or with a family history of familial adenomatous polyposis (FAP) or hereditary nonpolyposis colorectal cancer (HNPCC)
- 12) Patients who have not completed a national cancer screening program applicable to their sex and age (if it cannot be confirmed that the relevant test was received at a national cancer screening center or a recognized screening center)

However, if it is confirmed that the relevant test was received at a national cancer screening center or a recognized screening center during the screening period, and that the results were within normal range, the patients may participate in the clinical study.

Common to males and females: If a patient is \geq 50 years of age, the results of a colonoscopy within 5 years prior to the screening must be determined as being within normal range, and if adenomatous polyps are evident, the results of a colonoscopy within 1 year must be determined as being within normal range (inflammatory polyps or hyperplastic polyps are included in the normal range). If a patient is \geq 40 years of age, the results of a gastroscopy within 2 years prior to the screening must be within normal range. If a patient is \geq 54 years of age and has a 30 pack-year history of smoking or more, the results of a low-dose chest CT within 2 years prior to the screening must be within normal range. In case of liver cancer,

carriers of hepatitis B or hepatitis C virus and patients with hepatic cirrhosis fall under the exclusion criteria.

Females: For females ≥ 40 years of age, normal range findings must be confirmed in a mammogram within 2 years. For females ≥ 20 years of age, normal range findings must be confirmed in a Pap smear within 2 years.

- 13) Patients diagnosed with active pulmonary tuberculosis
- 14) Patients with HBV or HCV
- 15) Patients who test positive in human immunodeficiency virus (HIV) antibody test
- 16) Patients in an immunosuppressive state due to treatments such as immunosuppressants, chemotherapy, and radiotherapy
- 17) Patients with a history of mental disease within 6 months prior to the screening date, which may interfere with participation in the study
- 18) Patients who must take medications, that are known to have significant drug interactions within 14 days after the first administration of the investigational product or deemed unsuitable by the investigator's judgment
- 19) Individuals who participated in another clinical study* within 6 months before the time of screening

*Definitions

- · Drug: Those who participated in another clinical study within 6 months before the time of screening shall be excluded.
- · Medical device: Those who participated in a noninvasive clinical study may participate in this clinical study if the principal investigator determines that the safety or pharmacodynamic assessment will not be affected.
- 20) Individuals who have shown significant adverse events such as hypersensitivity reactions to the investigational product
- 21) Pregnant or breastfeeding females
- 22) Other individuals determined ineligible by the principal investigator to participate in the clinical study due to other reasons including clinical laboratory test results

5.3.4 **Assignment of Subject Numbers**

Subjects that will be voluntarily participating in this clinical study shall be assigned screening numbers (completion of informed consent form - checking eligibility with inclusion/exclusion criteria), and shall be assigned allocation numbers if they satisfy the inclusion/exclusion criteria.

PRT NO: VMCMT-001 Confidential 2021.06.07 Version :4.0 52 / 53

A screening number shall start with the letter "S" and consist of a five-digit number, and it shall be assigned base on the order of the subjects' written consent at the institution.

For example, the meaning of "S01001" is as follows:

Allocation numbers shall be assigned, in the order of enrollment in the clinical study, to the subjects who have satisfied the inclusion/exclusion criteria after completing all screening tests. The allocation number shall start with the letter "A" followed by a five-digit number.

For example, the meaning of "A01001" is as follows:

A	01	001
Allocation number (Acronym of allocation)	Institution (Indicated as "01" since it is a single center)	Allocation number

5.4 Contraindicated Medications

This clinical study shall be conducted in CMT1A patients with symptoms of weakness in lower limbs, and the list of contraindicated medications for CMT patients presented by the Charcot-Marie-Tooth Association (CMTA) and the CMT Research Foundation is as shown below. Since CMT is a congenital peripheral neuropathy that still does not have a cure, the best method is slowing the progression of disease. Neurotoxic drugs that can accelerate the damage of peripheral nerves shall be contraindicated, and the contraindicated medications are classified into 4 groups as shown in the following Table 5 depending on their risk level.

After the subjects sign the informed consent form, they shall be provided "Appendix 2. Contraindicated Medications" as an addendum.

Table 5. Contraindicated medications

Ingredient Name	Product Name	Indication
Definite High Risk		
Vinca alkaloids (vincristine)	Vincristine sulfate inject Vincran Injection,	tion, Acute leukemia, malignant lymphoma, malignant tumor
Taxols		
Paclitaxel	Taxol Injection, Pacli injection, Neotax Injec	taxel tion, Advanced prostate cancer

Ingredient Name	Product Name	Indication
	Sandoz Paclitaxel Injection	
Docetaxel	Taxotere Injection, Taxozen Injection, Dotaxel Injection	Breast cancer, prostate cancer, lung cancer
Cabazitaxel	Jevtana Injection	Breast cancer, lung cancer, ovarian cancer, esophageal cancer
Moderate to Significant Risk		
Amiodarone	Codarone Injection, Codarone Tablet	Ventricular arrhythm (fibrillation, tachycardia)
Arsenic trioxide	Trisenox Injection	Acute promyelocytic leukemia
Bortezomib	Velcade Injection, Tezobel Injection, Protezomib Injection	Multiple myeloma
Brentuximab vedotin	Adcetris Injection	Hodgkin lymphoma, systemic anaplastic large cell lymphoma
Cetuximab	Erbitux Injection	Head and neck cancer, colon cancer
Cisplatin	Cisplan Injection, Unistin Injection	Bladder cancer, ovarian cancer, testicular cancer
Colchicine	Colchicine Tablets, Colchinine Tablets	Gout prevention, gouty arthritis
Dapsone	Dapsone Tablets	Bullous herpetiformis dermatitis, Hansen's disease
Didanosine; Dideoxyinosine (ddl)	Videx EC SR Capsule (distribution currently discontinued)	HIV infection
Dichloroacetate (DCA)	Dichloroacetate sodium	Chronic lactic acidosis
Disulfiram	Alcoholstop (distribution currently discontinued)	Alcohol dependence
Eribulin mesylate	Halaven Injection	Metastatic breast cancer
Ipilimumab	Yervoy Injection	Melanoma
Ixabepilone	Ixempra (distribution currently discontinued)	Metastatic or locally advanced breast cancer
Leflunomide	Arava Tablets, Rualba Tablets, Durova Tablets	Rheumatoid arthritis
Lenalidomide	Revlimid Capsule, Lenaloma Capsule, Lenalid Tablets	Myelodysplastic syndrome
Metronidazole	Flasinyl Tablets, Trizele Injection, Flagyl Injection	Bacterial infection of large intestine, small intestine, vagina, and others; bacteremia, peritonitis, endocarditis
Misonidazole	F-18 fluoromisonidazole	PET/PET-CT imaging radiotracer
Nitrofurantoin; Macrodantin	Boryung Nitrofurantoin capsules	Urinary tract infection
Nitrous oxide		General anesthesia
Nivolumab	Opdivo Injection	Melanoma, advanced renal cell carcinoma
Oxaliplatin	Eloxatin Injection, Oxapla Injection, Oxaplin Injection	Colorectal cancer
Pembrolizumab	Keytruda Injection	Melanoma, non-small cell

Ingredient Name	Product Name	Indication
		lung cancer
Perhexiline	Pexsig (not distributed in South Korea)	Angina pectoris
Pomalidomide	Pomalyst Capsule	Multiple myeloma
Pyridoxine	Licopyri Injection, Vita B6 Injection, Plidoxine Tablets	When overdosed by 10X or more (indication: vitamin B6 deficiency, drug-induced neuropathy); However, there is no issue with intake through food.
Stavudine (d4T)	Zerit (distribution currently discontinued)	HIV infection
Suramin	Antrypol, Moranyl	African trypanosomiasis onchocerciasis
Thalidomide	Celgenethalidomide Capsule, Taligrov Capsule	Erythema, lepromatous nodules
Zalcitabine (ddC)	Hivid (distribution currently discontinued)	HIV infection
Fluoroquinolones		
Ciprofloxacin	Ciprobay Injection, Qupron Tablet, Cycin Injection	Bacterial infections (skin bone, blood, urinary tract respiratory, gastrointestina tract infections), pneumonia sinusitis, typhoid
Enoxacin	Flumark (distribution currently discontinued)	Urinary tract infection gonorrhea
Gatifloxacin	Gatiflo (distribution currently discontinued)	Pneumonia and bronchitis paranasal sinus, respiratory urinary tract infections sexually transmitted diseases
Levofloxacin	Levocacin Tablet, Levoroxin Injection, Levofexin Injection	Infections (skin, respiratory urinary tract), venerea diseases
Moxifloxacin	Avelox Injection, Remox Tablets, Moveloxin Injection	Infections (skin, respiratory)
Norfloxacin	Baccidal Tablets, Urekacin Capsule, Newsadal Tablets	Urinary tract infection prostatitis, gonorrhea
Ofloxacin	Fugacin Tablets, Effexin Injection, Ofloxacin Tablets	Infections (urinary tract, skin, bone, cardiac)
Sparfloxacin	Sparoxin (distribution currently discontinued)	Lower respiratory tract infection
Trovafloxacin (Alatrofloxacin)	Trovan (distribution currently discontinued)	Pneumonia, infections (abdomen, pelvis, skin)
Gold salts		
Auranofin	Ridaura (distribution currently discontinued)	Rheumatoid arthritis
Aurothioglucose	Solganal (distribution currently discontinued)	Rheumatoid arthritis
Gold sodium thiomalate	Aurolate (distribution currently discontinued)	Rheumatoid arthritis

Ingredient Name	Product Name	Indication
5-fluorouracil	Efficil-Injection	Breast cancer, colorecta cancer, gastric cancer pancreatic cancer
Doxorubicin	Adriamycin-PFS Injection, Adriamycin-RDF Injection	Leukemia, lymphoma, malignant tumor
Almitrine	Vectarion (distribution currently discontinued)	Acute respiratory failure
Chloroquine	Araren phosphate, Araren hydrochloride (distribution currently discontinued)	Amebiasis, malaria
Cytarabine (Ara-C; cytosine arabinoside); Cytarabine liposomal	Cytarabine Injection, Cytosar-U Injection, DepoCyt Injection	Leukemia, lymphomatous meningitis
Ethambutol	Tambutol Tablets, Myambutol Tablets	Tuberculosis
Etoposide (VP-16)	Lastet Capsule, EPS Injection, Etopul Injection	Small cell lung cancer refractory testicular neoplasm
Gemcitabine	Gemzar Injection, Gemtan Injection, Gembin Injection	Non-small cell lung cancer pancreatic cancer
Griseofulvin	Fulvicin Tablets,	Dermatophytosis, tinea capitis tinea unguium
Altretamine	Hexalen (distribution currently discontinued)	Ovarian cancer
Hydralazine	Hydralazine HCl Injection	Hypertension
Ifosfamide	Holoxan Injection	Testicular germ cell tumor, osteosarcoma, soft tissue sarcoma
Infliximab	Remicade Injection, Remsima Injection, Remaloce Injection	Rheumatoid arthritis, Crohn's disease
Isoniazid (INH)	Aina Tablet, Yuhanzid Tablets	Tuberculosis
Lansoprazole	Lanozol Tablets, Lancid Capsule, Lanster Capsule	Peptic ulcer, gastroesophagea reflux disease, Zollinger-Ellison syndrome
Mefloquine	Lariam Tablets	Malaria prevention and treatment
Omeprazole	OMP Tablet, Omeprazole Capsule	Peptic ulcer, gastroesophagea reflux disease, Zollinger-Ellison syndrome
Penicillamine	Artamin Capsule	
Phenytoin	Phenytoin Tablets, Hydantoin Tablets, Phenytoin sodium injection	Epilepsy, convulsion, seizure
Podophyllin resin	Podocon-25, Podofin, Podofilm	External genital or perianal warts due to HPV
Tacrolimus (FK506)	Prograf Capsule, Tarimus Capsule, Tacrobel Injection	Prevention of organ transplant rejection (liver, kidney, and other organs)
Zimeldine	(distribution currently discontinued)	Depression
α-interferon	Roferon A Prefilled Injection, Interferon Alpha-2 Injection	Hepatitis B, hepatitis C, HPV warts, Kaposi sarcoma, rena cell carcinoma, malignant

Ingredient Name	Product Name	Indication
		melanoma (skin cancer), non- Hodgkin lymphoma
Sertraline	Zoloft Tablets, Seltra Tablets, Traline Tablets	Depression, panic attack, obsessive-compulsive disorder, post-traumatic stress disorder, social disorder
Statins		
Atorvastatin	Lipitor Tablets, Atosta Tablets, Lipikhan Tablets	Hypercholesterolemia
Fluvastatin	Lescol Capsule, Lescol XL Tablets, Xilep Capsule	Hypercholesterolemia
Lovastatin	Lovastatin Tablets, Lovalord Tablets, Byrotin Tablets	Hypercholesterolemia
Pravastatin	Mevalotin Tablets, Prastan Tablets, Pravastar Tablets	Hypercholesterolemia
Rosuvastatin	Crestor Tablets, Rosvatin Tablets, Allstatin Tablets	Hypercholesterolemia
Simvastatin	Zocor Tablets, Simvast Tablets, Newvastin Tablets	Hypercholesterolemia
Negligible or Doubtful Risk		
Allopurinol	Zyroric Tablets, Allopurinol Tablets	Gout, gouty arthritis nephrolithiasis, urolithiasis
Amitriptyline	Elavil Tablets, Enafon Tablets, Amitriptyline HCI Tablets	Depression
Chloramphenicol	Helocetin Injection	Meningitis, typhoid
Chlorprothixene	Taractan (distribution currently discontinued)	Psychosis
Cimetidine	Tagamet Injection, Cimetidine Tablets H-2 Tablets	Gastric and duodenal ulcers gastroesophageal reflux
Clioquinol	Vioform (ointment, cream, ear drops)	dermatitis, folliculitis, eczema, tinea pedis, tinea cruris, dermatophytosis
Clofibrate	Atromid (distribution currently discontinued)	Hyperlipidemia
Cyclosporin A	Sandimmun Injection, Cipol Injection, Thymune Injection	Prevention of organ transplant rejection, severe psoriasis and rheumatoid arthritis
Enalapril	Ecaril Tablets, Enaprin Tablets, Pril Tablets	Hypertension, congestive heart failure
Gluthethimide	Doridem (distribution currently discontinued)	Insomnia
Lithium	Lithium carbonate Tablets, Lithan Tablets	Bipolar disorder
Phenelzine	Nardil (distribution currently discontinued)	Depression
Propafenone	Ritmol Tablets, Rytmonorm SR Capsule, Profenone Tablets	Atrial fibrillation, ventricular arrhythmia
Sulfonamides		
Sulfacetamide	Rosula Aqueos gel, Sulfaclan lotion	Acne, seborrheic dermatitis, eye and vaginal infections
Sulfabenzamide	Sultrin cream	Vaginitis

Ingredient Name	Product Name	Indication
Sulfadiazine	Virocide tablets (not distributed in South Korea)	Toxoplasmosis
Sulfamethoxazole	Vactoral Tablets	Urinary tract infection, otitis media
Sulfasalazine	Sazopin Tablets, Jopirin Enteric Coated Tablets, Salazine Tablets	Rheumatoid arthritis, ulcerative colitis
Sulfathiazole	Sultrin cream	Vaginitis
Sulfisoxazole (Sulfafurazole)	Gantrisin, Neoxazol, Sulfizole tablet	Urinary tract infection, otitis media

5.5 Termination of Clinical Study

5.5.1 Study Termination for Subjects

If a subject has completed all tests corresponding to the assessment index throughout the study period of 270 days (9 months) according to this clinical study protocol, the subject shall be deemed to have terminated the study.

5.5.2 Subject Drop-out

The subjects may withdraw their consent for study participation at any time during the clinical study, and they shall not face any disadvantages even if they do so. In addition, if the investigator determines that continuing to participate in the clinical study is harmful to a subject or that a subject refuses to follow the instructions of the investigator, the clinical study for the subject may be discontinued.

The study may be suspended for the following reasons:

- Adverse events that require discontinuation of the study (before treatment)
- A subject is lost to follow-up
- · Decision of the subject
- Decision of the investigator
- Other reasons

All reasons for the study discontinuation of subjects shall be recorded in the study termination form of the case report form.

5.5.3 Early Termination of Clinical Study

The sponsor has the right to discontinue the clinical study at any time throughout the clinical study for reasons such as safety, ethics, or management issues.

(1) Early discontinuation by the sponsor or investigator

This clinical study may be discontinued early at any time for safety, behavioral, or administrative reasons depending on the decision of the investigator or the sponsor.

The cases in which the investigator or the sponsor early discontinues the clinical study are as follows:

- 1) If the institution fails to enroll the target number of subjects;
- 2) If efficacy and safety information that can significantly impact the continuation of the clinical study emerges;
- 3) If it is difficult to conduct an appropriate clinical study because the institution or the investigator has violated the Korea Good Clinical Practice (KGCP), the clinical study protocol, contractual matters, etc.;
- 4) If there are other administrative reasons that can have a significant impact on the continuation of the clinical study.

(2) Permanent discontinuation of administration of investigational product

The cases in which administration of the investigational product is permanently discontinued are as follows but are not limited thereto:

- 1) If the subject or his or her representative withdraws consent;
- 2) If it is difficult to continue the clinical study due to adverse events;
- If violations of the inclusion and exclusion criteria are found while conducting the clinical study;
- 4) If it is determined that taking contraindicated medications or treatment with contraindicated pharmaceuticals is necessary;
- 5) If contraindicated therapies were performed, or if it is determined that performing contraindicated therapies is necessary;
- 6) If subject follow-up is not possible;
- 7) If serious violations of the protocol are found;
- 8) If another disease is found in the subject that makes it impossible to conduct the tests and procedures performed at regular visits;
- 9) If the investigator determines that continuing the clinical study is difficult due to other reasons.

In order not to miss the occurrence of adverse events which the investigator does not know about, all methods such as phone calls, letters, and direct visits shall be utilized to directly contact the subjects who refuse to visit. The reasons for early discontinuation or termination of administration shall be recorded in the case report form. Subjects who have early discontinued or have terminated administration may not participate again.

For subjects who have early terminated the study, the tests for early termination in "Summary of Study Schedule" shall be performed.

If the clinical study has been early discontinued, the following shall be performed:

- 1) If the principal investigator has early terminated or suspended the clinical study without a prior agreement with the sponsor, the principal investigator shall immediately inform this fact to the sponsor and the Institutional Review Board, and shall submit a detailed statement of reasons for the early termination and suspension.
- 2) If the sponsor has early terminated or suspended the clinical study, the principal investigator shall immediately inform this fact to the Institutional Review Board, and shall submit a detailed statement of reasons for the early termination and suspension.
- 3) If the Institutional Review Board has early terminated or suspended the clinical study, the principal investigator shall immediately inform this fact to the sponsor, and shall submit a detailed statement of reasons for the early termination and suspension.
- 4) If the relevant clinical study has been early terminated or suspended as in 1) through 3) in accordance with regulations, the principal investigator shall immediately inform this fact to the subjects, and shall ensure that appropriate measures are taken and follow-ups are conducted.

[figure not shown]
For subjects who have been discontinued due to adverse events, follow-ups shall be conducted until the investigator determines that the corresponding adverse events are resolved or the subjects are medically stable. For these subjects, Helixmith Co., Ltd. and the investigators shall try their best to provide standard clinical treatment. Helixmith Co., Ltd. shall provide indemnification, if applicable, in accordance with the subject indemnification policy. In addition, the tests (10 items) mentioned above shall be performed for the safety of the subjects.

If a subject cannot be contacted in follow-ups, the investigator shall attempt to contact (phone call, email, etc.) the subject at least three times. If there is no response from the subject despite this, the investigator shall contact a family member of the subject or his or her primary physician. The evidence of such attempted contact shall be recorded in the source data, and the confirmation of receipt of letters sent to the subject can be an example of such proof.

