7.4.3 Reporting, collection, and recording of AEs

The principal investigator must educate the sub-investigator and subjects or representatives of the subject about all adverse events that may occur after the administration of the investigational product and educate them to report all reactions that occur after administration.

- All AEs that occur from administration of investigational product to follow-up visits (until end of the clinical trial) are collected. However, if a sign, symptom, or disease that occurred before the administration is worsened after the administration, it shall also be considered an AE.
- An AE must be reported including the name of the AE, start date and end date, severity, actions related to investigational product, progress, causality with the investigational product, remedial treatment, and whether it is an SAE.
- When documenting an AE, the investigator uses a comprehensive diagnosis or symptom name using standard medical terminology instead of each symptom or sign.
- 4) AEs are observed for the study period of nine months (day 0 to 270). If an AE or SAE that occurs within the nine-month follow-up period is not resolved within this period, follow-up shall be conducted until the AE is resolved.

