8.3 Classification of Subjects

Screen Failure - This is a subject who has signed the informed consent form in the clinical study but failed to satisfy the inclusion/exclusion criteria in the screening process. No follow-up for safety or pharmacodynamic assessment shall be conducted, neither shall any other clinical study procedure be performed.

Evaluable Subject - These are all of the subjects who have been administered the investigational product by participating in the clinical study. They shall be classified according to the definition of "8.1 Analysis Set" and analyzed.

Lost to Follow-up - This is a subject who has been administered the investigational product, but has not completed the planned visits. These include subjects who have withdrawn consent as well as subjects who have refused further participation in the clinical study and failed to respond to all attempts at contacting the subjects. Analysis shall be performed according to "8.2. Handling of Missing Values."

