#### 2.2.2 Per Protocol Set (PPS)

PPS shall include those subjects in the ITT set who have completed the clinical study according to the clinical study protocol without major protocol violations. Subjects who fall under the following shall be defined as PPS. The violation of eligibility in condition number  $\widehat{(1)}$  of PPS shall be determined in a data review meeting prior to

datalock.

- ① Subjects who have not violated the inclusion and exclusion criteria (eligible patients)
- Subjects who have completed all visits

Analysis shall also be performed on PPS by using the auxiliary analysis sets to analyze the sensitivity of the efficacy assessment.

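### Protocol 5.5.3(2) stops dosing for good without keeping the subject on the visits to Day 270, and the per-protocol set does not require the four doses (minor)

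*Protocol*

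**What the plan says.** **Dosing stops.** Protocol 5.5.3(2) introduces nine reasons with "The cases in which administration of the investigational product is permanently discontinued are as follows but are not limited thereto". Item 4 reads "If it is determined that taking contraindicated medications or treatment with contraindicated pharmaceuticals is necessary". Items 1 and 6 (consent withdrawn, follow-up impossible) end observation by their nature. Items 2, 4, 5, 7 and 9 need not.

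**What follows a stop.** The text after the list says "Subjects who have early discontinued or have terminated administration may not participate again". Early-termination tests are assigned to subjects who have left the study early. Continued follow-up is described this way: "For subjects who have been discontinued due to adverse events, follow-ups shall be conducted until the investigator determines" that the event has resolved or the subject is stable. The section also asks for calls, letters and visits to subjects who refuse to attend, and at least three contact attempts when a subject cannot be reached.

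**Observation and completion.** Protocol 7.4.3 sets a general adverse-event window of Day 0 to Day 270, with unresolved events followed to resolution. Protocol 5.5.1 defines finishing the study by tests completed over 270 days and does not mention doses. Protocol 8.3 defines lost to follow-up as "This is a subject who has been administered the investigational product, but has not completed the planned visits".

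**Per-protocol set (PPS).** Protocol 8.1.3 and SAP 2.2.2 require completion according to the protocol without major violations. They then list two conditions: no eligibility violation, and "Subjects who have completed all visits". Neither document sets a number of doses. SAP 2.2.2 uses the PPS as the sensitivity analysis for efficacy.

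**The concern.** Stopping the drug and leaving the study are different events, and 5.5.3(2) does not separate them. The primary objective is safety after repeated doses, observed for 270 days in 12 subjects. If a required stop also removes the subject from the schedule, later laboratory tests, vital signs and visits are lost in a subject who could still have been observed. That subject stays in the safety-set denominator, because SAP 2.1.1 needs only a dose and assessable safety. SAP 4.7 plans crude percentages over that denominator.

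If the subject remains on the schedule, the question moves to efficacy. The PPS is the only planned check on the ITT result in a study of repeated doses, yet its listed conditions can be met without the repeated doses.

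Item 4 is a realistic trigger. Protocol Table 5 lists fluoroquinolones, metronidazole, nitrofurantoin, omeprazole and statins. Table 18 lists urinary tract infection among the frequent events (5% or more) of earlier studies, and several Table 5 drugs are listed for that indication. How often a stop occurred here is not documented.

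**Working it through.** The plan has no figure to reproduce: the 12 subjects are set by precedent (Protocol 5.3.1). The check sets the texts side by side and then sizes the consequence.

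**1. Which reading?**
- *Exit:* the heading of 5.5.3 is early termination of the study; several items are framed around continuing the study; subjects whose administration has ended are barred from participating again.
- *Stay:* Protocol 7.4.5 and 7.4.6 record permanent discontinuation of the drug as an action on treatment, separate from the study termination form in 5.5.2; the early-termination tests are tied to leaving the study, not to stopping the drug; completion in 5.5.1 does not depend on doses.

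No sentence chooses. Exit has the stronger textual support.

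**2. Follow-up lost on exit.** Days lost = 270 − stop day; planned total = 12 × 270 = 3,240 subject-days.

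| Stop day | Days lost | Share of subject's 270 | Share of 3,240 |
|---|---|---|---|
| 14 | 256 | 94.8% | 7.9% |
| 90 | 180 | 66.7% | 5.6% |
| 104 | 166 | 61.5% | 5.1% |

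An exit at Visit 3 replaces Visits 4 to 7 with one early-termination visit.

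**3. Effect on a crude adverse-event percentage.** Assumptions: true 270-day risk R = 30%, constant hazard, exit at Day 52 (the mean if stops are uniform over Days 0 to 104). Observed risk in a leaver: 1 − 0.7^(52/270) = 6.6%. Crude incidence with k leavers = [(12 − k) × 30% + k × 6.6%]/12:
- k = 1: 28.1%
- k = 2: 26.1%
- k = 3: 24.2%

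For scale, the Clopper-Pearson 95% interval for 4 of 12 is 9.9% to 65.1%. For a zero-event finding, the upper limit is 1 − 0.025^(1/n): 26.5% for 0/12 and 28.5% for 0/11, the latter if one subject cannot be evaluated to Day 270.

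**4. Effect on the PPS if the subject stays.** Planned dose is 4 × 14 = 56 mg. One dose is 14 mg (25%); two doses are 28 mg (50%). With response proportional to dose (assumption), a PPS of 12 with one such subject has a mean change, as a share of the four-dose value, of:
- one dose: (11 + 0.25)/12 = 93.8%
- two doses: (11 + 0.50)/12 = 95.8%
- one dose and no response at all: 11/12 = 91.7%

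Under the same uniform assumption, 14/104 = 13.5% of stops fall before the second dose and (90 − 14)/104 = 73.1% between the second and third, so two doses is the likelier case.

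**5. Does the reporting reveal it?** SAP 4.5.1 lists drop-outs. SAP 4.5.3 lists completers excluded for violations. SAP 4.7 tabulates actions on the drug only for adverse events. A subject stopped under item 4 who stays and enters the PPS appears in none of these. The SAP plans no table of administrations received.

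**The case against.** The strongest reply is that the documents give more protection than the gap suggests, and much of it stands.

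- **Follow-up is not abandoned.** A reader might infer that safety observation simply ends after a non-adverse-event stop. The text does not support that. The contact rules in 5.5.3 are not limited to adverse-event stops, 7.4.3 follows unresolved events to resolution, and study leavers get an early-termination visit. What these do not supply is the remaining scheduled laboratory tests, vital signs and visits.
- **The Day 0 to 270 window is not contradicted.** A general observation window does not conflict with some subjects leaving early.
- **PPS entry is possible, not certain.** A reader might infer that a one-dose subject will be in the PPS. The lead-in excludes major violations, Visits 3 to 5 are titled as administrations, and SAP 2.4 sends the sets to a data review meeting before datalock. That meeting could exclude the subject. But a stop that the protocol itself requires is hard to call a violation, and no dosing rule is written down for the meeting to apply.
- **The two harms are alternatives.** A subject who leaves fails the all-visits condition; a subject who stays loses no scheduled safety visits.
- **The sizes are small and depend on assumptions.** Constant hazard fits poorly for injection site reactions, which Protocol 7.2.2 defines as occurring within 24 hours of injection. The study is descriptive with 12 subjects.
- **Keeping such subjects has a price.** Someone who starts a neurotoxic drug contributes Day 270 nerve conduction and severity scores that are confounded by it. This stands, and the fix has to make it visible.

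**Conclusion.** The point holds as a minor one. 5.5.3(2) stops dosing for reasons that need not end observation, and its better-supported reading removes the subject from the remaining scheduled safety visits: 256 of 270 days for a stop at Day 14, 166 for a stop at Day 104. On the other reading, the listed PPS conditions admit a subject without the four doses unless the data review meeting intervenes.

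A reader might go further and infer that the planned adverse-event percentages are materially understated. The documents do not support that. No affected subject is documented, and the illustrative shift from 30% to 28.1% with one leaver is small beside the precision available from 12 subjects. The shifts rest on the assumed hazard, stop times and dose-response. If every subject received four doses, nothing changes.

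One limit: a figure in 5.5.3 is not shown in the available text, and the section refers to ten test items. That reference is attached to adverse-event discontinuations, so it would not settle a stop under item 4.

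**What to change.** Keep every stopping rule and make three changes.

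1. **Protocol 5.5.3(2).** State that a subject whose dosing is permanently stopped receives no further product but attends the remaining visits to Day 270 for safety assessments, and for efficacy assessments where feasible. Exempt subjects who withdraw consent, for whom follow-up or the tests are impossible (items 6 and 8), or for whom the investigator judges continued participation harmful (5.5.2). Replace the bar on participating again with a bar on receiving the product again or being re-enrolled.
2. **Protocol 8.1.3 and SAP 2.2.2.** Add a third PPS condition: received all four administrations.
3. **SAP reporting.** Tabulate subjects by number of administrations received. List those with fewer than four, with the reason, last day observed and any contraindicated drug started, so that their Day 270 efficacy data can be read with that confounding in view.

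Protocol 5.7.1 says enrolment is complete. If all visits are also over, make only the SAP changes, before datalock.

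Cost: one paragraph and one wording change through the normal amendment route (Protocol section 16), plus one PPS condition, one small table and one listing. No visits are added to the schedule. The PPS may be smaller; membership of the ITT and safety sets does not change.
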